6.4. Follow-Up

6.4.1. Safety Follow-Up

The safety follow-up period is the interval between the EOT visit and the scheduled follow-up visit, which should occur 30 days (+ 7 days) and 60 days (+ 7 days) after the last dose of study treatment. Monitoring for the occurrence of new AEs should be continued for at least 60 days after the last dose of study treatment or until the start of new anticancer therapy, whichever occurs first. Reasonable efforts should be made to have the subject return for the follow-up visits and report any AEs that may occur during this period. If a subject is scheduled to begin a new anticancer therapy before the end of the 30-day or 60-day safety follow-up period, the safety follow-up visit should be performed before new anticancer therapy is started. Once new anticancer therapy has been initiated, AEs and SAEs will no longer be collected, and the subject will move into the survival follow-up period.

Note: As of Protocol Amendment 5, the safety follow-up visits will include AE and concomitant medication assessment only and may be completed remotely (such as by televisit).

Note: As of Protocol Amendment 5, if a new anticancer therapy has been initiated before the end of the safety follow-up period, no further survival follow-up assessment will be required beyond the last safety follow-up visit.

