8.1.2. Reporting

Adverse events that begin or worsen after informed consent should be recorded on the Adverse Events form of the eCRF. Conditions that were already present at the time of informed consent should be recorded on the Medical History form in the eCRF. Monitoring for the occurrence of new AEs should be continued for at least 60 days after the last dose of study treatment or until the start of new anticancer therapy, whichever occurs first. Adverse events (including laboratory abnormalities that constitute AEs) should be described using a diagnosis whenever possible rather than by individual underlying signs and symptoms.

The disease/disorder being studied, or expected progression, signs, or symptoms of the disease/disorder being studied, should not be reported as an AE/SAE unless it is considered more severe than expected for the participant's condition or considered to be treatment-related by the investigator. Additionally, efficacy endpoints as outlined in Section 2.2 will not be reported as AE/SAEs, specifically, any event that is related to disease progression of the cancer under study. Unblinded aggregated efficacy endpoint events and safety data will be monitored to ensure the safety of the subjects in the study. Any suspected endpoint that upon review is not progression of the cancer under study will be forwarded to Incyte Pharmacovigilance as an SAE within 24 hours of determination that the event is not progression of the cancer under study.

The severity of AEs will be assessed using CTCAE v4.03 Grades 1 through 5. If an event is not classified by CTCAE, the severity of the AE will be graded according to the scale below to estimate the grade of severity:

Grade 1	Mild; asymptomatic or mild symptoms; clinical or diagnostic observations only; intervention not indicated.
Grade 2	Moderate; minimal, local, or noninvasive intervention indicated; limiting age-appropriate activities of daily living.
Grade 3	Severe or medically significant but not immediately life-threatening; hospitalization or prolongation of hospitalization indicated; disabling; limiting self-care activities of daily living.
Grade 4	Life-threatening consequences; urgent intervention indicated.
Grade 5	Death due to AE

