#### **7.3.7. Progression-Free Survival**

Progression-free survival is defined as the length of time between the baseline visit (Day 1) and the earlier of death or PD as assessed by RECIST v1.1 and mRECIST v1.1. Date of death will be determined using the Death Report CRF.

Censoring for PFS will follow the algorithm outlined in [Table 7](#) which is based on the FDA – Guidance for Industry: Clinical Trial Endpoints for the Approval of Cancer Drugs and Biologics (FDA 2007).

Kaplan-Meier curves for PFS will be presented by cohort-specific tumor types. The KM estimate of median PFS will be presented with its 95% CI. The 95% CI will be calculated using the Brookmeyer and Crowley's method ([Brookmeyer and Crowley 1982](#)).

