- Summary of TEAEs leading to INCAGN01876 dose reduction by SOC and PT
- Summary of TEAEs leading to any dose interruption by SOC and PT
- Summary of TEAEs leading to discontinuation of INCAGN01876 by SOC and PT
- Summary of treatment-emergent irAEs (investigator identified) by SOC and PT
- Summary of treatment-emergent irAEs (sponsor identified) by SOC and PT
- Summary of treatment-emergent irAEs (investigator identified) by SOC, PT, and maximum severity
- Summary of Grade 3 or higher treatment-emergent irAEs (investigator identified) by SOC and PT
- Life table estimate of time to first Grade 3 or higher TEAEs
- Summary of TEAEs leading to death by SOC and PT
- Summary of infusion reactions

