3.2.15.1	Summary of Treatment-Emergent Adverse Events Leading to Discontinuation of INCAGN01876 by MedDRA System Organ Class and Preferred Term - by Treatment Group and Dose	Phase 1 FAS Population	X	
3.2.15.2	Summary of Treatment-Emergent Adverse Events Leading to Discontinuation of INCAGN01876 by MedDRA System Organ Class and Preferred Term - by Treatment Group and Tumor Type	Phase 2 FAS Population	X	
3.2.16.1	Summary of Treatment-Emergent Immune-Related Adverse Events (Investigator Identified) by MedDRA System Organ Class and Preferred Term - by Treatment Group and Dose	Phase 1 FAS Population	X	
3.2.16.2	Summary of Treatment-Emergent Immune-Related Adverse Events (Investigator Identified) by MedDRA System Organ Class and Preferred Term - by Treatment Group and Tumor Type	Phase 2 FAS Population	X	
3.2.17.1	Summary of Treatment-Emergent Immune-Related Adverse Events (Sponsor Identified) by MedDRA System Organ Class and Preferred Term - by Treatment Group and Dose	Phase 1 FAS Population	X	
3.2.17.2	Summary of Treatment-Emergent Immune-Related Adverse Events (Sponsor Identified) by MedDRA System Organ Class and Preferred Term - by Treatment Group and Tumor Type	Phase 2 FAS Population	X	
3.2.18.1	Summary of Treatment-Emergent Immune-Related Adverse Events (Investigator Identified) by MedDRA System Organ Class, Preferred Term, and Maximum Severity - by Treatment Group and Dose	Phase 1 FAS Population	X	
3.2.18.2	Summary of Treatment-Emergent Immune-Related Adverse Events (Investigator Identified) by MedDRA System Organ Class, Preferred Term, and Maximum Severity - by Treatment Group and Tumor Type	Phase 2 FAS Population	X	

Table No.	Title	Population	Standard	In-Text
3.2.19.1	Summary of Grade 3 or Higher Treatment-Emergent Immune-Related Adverse Events (Investigator Identified) by MedDRA System Organ Class and Preferred Term - by Treatment Group and Dose	Phase 1 FAS Population	X	X
3.2.19.2	Summary of Grade 3 or Higher Treatment-Emergent Immune-Related Adverse Events (Investigator Identified) by MedDRA System Organ Class and Preferred Term - by Treatment Group and Tumor Type	Phase 2 FAS Population	X	X
3.2.20	Life Table Estimate of Time to First Grade 3 or Higher Treatment-Emergent Adverse Event - by Treatment Group and Tumor Type	Phase 2 FAS Population	X	
3.2.21.1	Summary of Adverse Events With a Fatal Outcome by System Organ Class and Preferred Term - by Treatment Group and Dose	Phase 1 FAS Population	X	

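### The planned life table of time to first Grade 3 or higher TEAE has no stated rule for death; if progression deaths count as withdrawals, its complement is at or above the cumulative incidence

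*SAP*

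**What the plan says.** SAP 8.2.5 names a "Life table estimate of time to first Grade 3 or higher TEAEs" in its list of AE summaries. SAP Appendix A repeats it as Table 3.2.20, "Life Table Estimate of Time to First Grade 3 or Higher Treatment-Emergent Adverse Event - by Treatment Group and Tumor Type", for the Phase 2 full analysis set. The SAP says nothing else about this analysis.

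The efficacy endpoints are specified more fully. SAP 7.3.7 states that "Censoring for PFS will follow the algorithm outlined in" its Table 7, SAP 7.3.3 applies the same algorithm to duration of response, and SAP 7.3.8 gives a censoring rule for OS. In all of these, and in duration of disease control (SAP 7.3.4), death is part of the event.

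Three protocol rules determine who can have a recorded event:

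- **AE window (Protocol 8.1.2).** New AEs are monitored "for at least 60 days after the last dose of study treatment or until the start of new anticancer therapy, whichever occurs first".
- **New therapy (Protocol 6.4.1).** "Once new anticancer therapy has been initiated, AEs and SAEs will no longer be collected".
- **Progression (Protocol 8.1.2).** The protocol says that "efficacy endpoints as outlined in Section 2.2 will not be reported as AE/SAEs". The sentence before this one excludes the disease under study and its expected progression "unless it is considered more severe than expected for the participant's condition or considered to be treatment-related by the investigator". The exclusion of endpoints is then spelled out as covering "specifically, any event that is related to disease progression of the cancer under study".

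**The concern.** A subject who dies of progression without an earlier Grade 3 or higher TEAE normally has no Grade 5 TEAE and can never have a first severe TEAE. A single-event life table has only one place for that subject, among the withdrawals. It then gives the subject the later toxicity experience of those still under observation, although none is possible after death. Read as the proportion of treated subjects who have a severe TEAE, the complement of the curve is too high, or at best equal.

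Frequency and severity of AEs are a primary endpoint (SAP 2.3.1). SAP Table 3.2.5.2 gives crude Grade 3 or higher incidence in the same population. The report could therefore show two figures for what looks like the same risk, with nothing to explain why they differ.

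**Working it through.** The plan states no figure for this analysis, so there is none to reproduce. The check has three parts.

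**1. Direction for death.** Let λ1(t) be the hazard of a first severe TEAE and λ2(t) the hazard of death without one, among subjects with neither. With S1 = exp(−∫λ1) and S2 = exp(−∫λ2):

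- life-table complement with deaths withdrawn = ∫ λ1 S1 dt = 1 − S1
- cumulative incidence = ∫ λ1 S1 S2 dt

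S2 never exceeds 1, so the first is never below the second. This needs neither constant hazards nor independence.

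**2. Size for death (illustration).** Inputs:

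- Net TEAE risk over the horizon: 33%, borrowed from Protocol 1.3.2.2. There it is a treatment-related Grade 3 or 4 rate in first-line NSCLC on nivolumab plus ipilimumab, not an all-cause TEAE rate in this trial.
- Net risk of competing death before a severe TEAE and inside the AE window: not in the documents; assumed 5%, 10%, 20% or 40%.
- Constant hazards, with the horizon scaled to 1.

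Formulas: L1 = −ln(1 − 0.33) = 0.4005; L2 = −ln(1 − net death risk); life-table complement = 1 − exp(−L1) = 33.0%; cumulative incidence = L1/(L1 + L2) × (1 − exp(−(L1 + L2))).

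Example at 20%: L2 = 0.2231 and L1 + L2 = 0.6236. Then exp(−0.6236) = 0.67 × 0.80 = 0.536, and the cumulative incidence is 0.4005/0.6236 × 0.464 = 29.8%.

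| Net competing death | Life-table complement | Cumulative incidence | Excess (points) |
|---|---|---|---|
| 5% | 33.0% | 32.2% | 0.8 |
| 10% | 33.0% | 31.4% | 1.6 |
| 20% | 33.0% | 29.8% | 3.2 |
| 40% | 33.0% | 26.3% | 6.7 |

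A simulated actuarial life table (12 monthly intervals, withdrawals counted as half, 400,000 subjects) agrees with the closed form: 33.0% against 31.5% at 10% competing death.

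The size depends on the assumed TEAE risk. At 68.7%, the Grade 3 or 4 AE rate that Protocol 1.3.2.2 gives for a different nivolumab plus ipilimumab schedule, the excess runs from 1.4 points (5% competing death) to 12.3 points (40%).

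**3. New anticancer therapy.** This ends recording but does not prevent toxicity. The same simulation used a 33% net TEAE risk, 60% net exit to new therapy and almost no deaths. Dependence was induced by a gamma frailty of variance 1, which also lowers the average TEAE risk.

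| Exit to new therapy | Life table | TEAE risk regardless of new therapy |
|---|---|---|
| Independent of TEAE risk | 33.1% | 33.1% |
| Sooner in higher-risk subjects | 22.6% | 28.6% |
| Sooner in lower-risk subjects | 33.8% | 28.5% |

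If the target is instead the share with a severe TEAE recorded before new therapy, the life table is above it: 33.1% against 22.3% under independence. The direction therefore depends on the estimand and, for the first target, on how exit relates to risk.

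**The case against.** **Censoring is inferred, not written.** The SAP never says that progression deaths are withdrawn. Table 3.2.20 is marked as a standard table, and Appendix A refers standard tables to a separate conventions document that is not among the files, so a rule may exist there. This stands. What can be documented is that the SAP states no rule. The direction of bias is conditional on the ordinary single-event reading of the method it names.

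**Not every progression death is lost as an event.** The exception quoted from Protocol 8.1.2 lets some progression-related events be reported, and a fatal TEAE is Grade 5 and counts. Protocol 8.3.2 also asks for SAEs regardless of suspected cause, progression included, but gives way where the protocol specifies otherwise, as 8.1.2 does. This reduces the number of misclassified deaths without removing them.

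**Few such deaths may fall in the window.** Treatment may continue past first progression (Protocol 7.7.1), and many deaths may come after AE collection has closed, when the subject has already left the risk set. This stands, and it is why no size can be claimed for this trial.

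**Little depends on the table.** It is descriptive and not marked for in-text use. Crude Grade 3 or higher incidence appears separately in Tables 3.2.5.1 and 3.2.5.2. This stands too.

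**Risk under continued observation is a legitimate target.** It is for new therapy and the 60-day limit, where toxicity remains possible. It is much harder to interpret for death.

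**Conclusion.** The point holds in a limited form. A single-event life table is planned with no time origin, censoring rule or handling of death. If progression deaths are withdrawn, its complement is at or above the cumulative incidence of severe TEAEs. Under the stated assumptions (constant hazards, 33% net TEAE risk, 5% to 40% net competing death) the excess is about 1 to 7 points. The true size cannot be derived from the documents.

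A reader might infer three stronger conclusions that the documents do not support:

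- **That the trial overstates severe toxicity.** Only one descriptive Phase 2 table is affected, and the crude incidence tables are not.
- **That stopping AE collection at new therapy or 60 days after the last dose also biases the curve upward.** That bias can be upward, downward or nil.
- **That the curve conflicts with the 40% toxicity limit.** That rule (Protocol 4.1.2; SAP 3.2) uses the percentage of subjects in a treatment group with INCAGN01876-related Grade 3 or higher AEs. Table 3.2.20 counts all-cause TEAEs by treatment group and tumor type and does not feed the rule.

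The change is worth making because it is cheap and gives a number that can be read as a risk, but no trial decision turns on it.

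**What to change.** In SAP 8.2.5 and Table 3.2.20:

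1. Replace the life table with the Aalen-Johansen cumulative incidence of first Grade 3 or higher TEAE, measured from Day 1.
2. Treat death without a prior Grade 3 or higher TEAE as a competing event.
3. State that subjects are censored at the end of AE collection (new anticancer therapy or 60 days after the last dose), at data cutoff or at loss to follow-up.
4. Add a sensitivity analysis that treats the end of AE collection as a competing event. It targets the share of treated subjects with a recorded severe TEAE, so it is the version to set beside the crude percentages.

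The cost is a short SAP addition and one changed table program, with no new data. The curve then reads as observed risk in the presence of death, not as risk in a setting where nobody dies of progression.

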### **8.3. Clinical Laboratory Tests**

#### **8.3.1. Laboratory Value Definitions**

Laboratory values and change from baseline values will be summarized descriptively by visit. Baseline will be determined according to Section 4.1.3. If there are multiple values that meet the criteria for baseline, additional rules may be provided after consultation with the medical monitor to delineate which value will be defined as baseline.

Laboratory test values outside the normal range will be assessed for severity based on CTCAE grade or similar criteria where clinical intervention is required for CTCAE grading. The incidence of abnormal laboratory values and shift tables relative to baseline will be tabulated.

#### **8.3.2. Laboratory Value Summaries**

Laboratory values and change from baseline values will be summarized descriptively by visit. The baseline value will be determined using the nonmissing values collected before the first dose, prioritizing scheduled assessments for baseline identification over unscheduled visits. The last record before administration in the highest priority will be considered the baseline record. For baseline laboratory candidates with the same date and time in the same priority category, additional rules may be provided after consultation with the medical monitor to delineate which value will be defined as baseline.

All test results and associated normal ranges from local laboratories will be reported in SI units. All tests with numeric values will have a unique unit per test. Any laboratory test results and

associated normal ranges from local laboratories will be converted to SI units. For the limited number of cases where the associated normal ranges from a local laboratory cannot be obtained despite due diligence, if query is unsuccessful at resolving the issue and analysis is mandatory then the clinical scientist and medical monitor can provide a suitable normal range to be used in determining CTC grading and flags for above and below normal.

When there are multiple laboratory nonmissing values for a subject's particular test at a scheduled visit, the laboratory value with the smallest laboratory sequence number will be used in by-visit summaries (Table 8).

**Table 8: Identification of Records for Postbaseline By-Visit Summaries**

Priority	Laboratory Visit	Proximity to Visit Window	Tiebreaker
1	Scheduled	In-window	Use smallest laboratory sequence number
2	Unscheduled	In-window	
3	Scheduled	Out-of-window	

Numeric laboratory values will be summarized descriptively in SI units, and non-numeric test values will be tabulated when necessary. In addition, line graphs and box-and-whisker plots will be provided for hemoglobin, platelet counts, white blood cells, and neutrophils.

For test results that will be summarized with available normal ranges, the number and percentage of subjects with the laboratory values being low (but never high), normal, high (but never low), and both low and high will be calculated for each test. This shift summary will be produced for each test for the safety population. The denominator for the percentage calculation will use the number of subjects in the baseline category (ie, low, high, normal, missing) as the denominator for the percentage in each of the categories during the treatment period.

In cases where differentials of hematology parameters are obtained without corresponding absolute count data, efforts will be made to investigate if the conversion to an absolute value will lead to additional abnormalities. This will be discussed with the clinical team regarding appropriate documentation and action.

#### 8.4. Vital Signs

Values at each scheduled visit, change, and percentage change from baseline for vital signs, including systolic blood pressure, diastolic blood pressure, pulse, respiration rate, and body temperature will be summarized descriptively.

Criteria for clinically notable vital sign abnormalities are defined in Table 9. The abnormal values for subjects exhibiting clinically notable vital sign abnormalities will be listed along with their assigned treatment group. Alert vital signs are defined as an absolute value outside the defined range and percentage change > 25%. The abnormal values for subjects exhibiting alert vital sign abnormalities will be listed.

**Table 9: Criteria for Clinically Notable Vital Sign Abnormalities**

Parameter	High Threshold	Low Threshold
Systolic blood pressure	> 155 mmHg	< 85 mmHg
Diastolic blood pressure	> 100 mmHg	< 40 mmHg
Pulse	> 100 bpm	< 45 bpm
Temperature	> 38°C	< 35.5°C
Respiratory rate	> 24/min	< 8/min

### 8.5. Electrocardiograms

Twelve-lead ECGs including heart rate, PR, QRS, QT, QTcF, QTcB, JTc, and RR intervals will be obtained for each subject at the screening, end of treatment, and safety follow-up visits during the study. Values at each scheduled visit, change, and percentage change from baseline will be summarized for each ECG parameter. Baseline will be determined as the average of all nonmissing values before the first administration of INCAGN01876, nivolumab, or ipilimumab.

Criteria for clinically notable ECG abnormalities are defined in [Table 10](#). Subjects exhibiting clinically notable ECG abnormalities will be listed with study visit and assigned treatment group. Abnormal values for subjects with alert ECG values, defined as both the absolute value and the percentage change from baseline being outside normal ranges, will be identified and listed.

**Table 10: Criteria for Clinically Notable Electrocardiogram Abnormalities**

Parameter	High Threshold	Low Threshold
QTcF	> 460 msec	< 295 msec
PR	> 220 msec	< 75 msec
QRS	> 120 msec	< 50 msec
QT	> 500 msec	< 300 msec
RR	> 1330 msec	< 600 msec

QTcF = Fridericia correction.

## **9. INTERIM ANALYSES**

### **9.1. Overview of Interim Analyses**

#### **9.1.1. Interim Analyses for Safety**

There will be no planned, formal interim analyses for the Phase 1 dose escalation portion of the study. The review of accrued clinical data will be conducted by Incyte and provided to study investigators via teleconferences at the end of Phase 1 of the study. Based on review of the most current safety data, the sponsor (in consultation with the study investigators and using the dose-escalation/de-escalation rules) will determine if and at what dose additional subjects should be treated in the study.

A DMC will be charged with evaluating interim safety results. The DMC will be comprised of members who are internal to the sponsor but not members of the study team. The DMC members will include a medical monitor who will serve as the DMC chair and meeting facilitator, the head of biostatistics or a designee, the head of regulatory affairs or a designee, and the study medical monitor who will be a nonvoting member. The DMC will meet at least every 6 months to review the rate of DLTs and irAEs in each treatment group and the overall safety of the subjects treated with INCAGN01876, nivolumab, and ipilimumab. Additional operational details of the interim analyses, including TFLs provided to the DMC, will be provided in the DMC Charter. Additional safety analyses may be performed at the discretion of the DMC chair.

Formal quarterly safety reviews will be conducted by the SMT to review safety data with the obligation to hold an SMT meeting on a quarterly basis. Per the Data Monitoring Charter, the DMC is obligated to meet at least every 6 months starting after the first 10 subjects have been dosed to review safety data with key tables, listings, and figures for review specified in the Data Monitoring Charter. During Phase 2, the study team will review efficacy and safety data every 6 months, with the key tables, listings, and figures for review also specified in the Data Monitoring Charter.

